## LIST OF ABBREVIATIONS

Abbreviation	Definition
AE	Adverse event
ALT	Alanine aminotransferase
ARC	Absolute reticulocyte count
AST	Aspartate aminotransferase
BFU-E	Burst-forming unit - erythroid
BL	Baseline
CFU-E	Colony-forming unit - erythroid
CNS	Central nervous system
CR	Complete response
CRF	Case report form
DBA	Diamond Blackfan anemia
DBAR	Diamond Blackfan Anemia Registry of North America
EoS	End of Study
EPO	Erythropoietin
FDA	Food and Drug Administration
FIH	First in human
GCP	Good Clinical Practice
Hb	Hemoglobin
HLA	Human leukocyte antigen
IA	Interim Analysis
IP	Intraperitoneal
MTD	Maximum tolerated dose
NCI-CTCAE	National Cancer Institute Common Terminology Criteria for Adverse Events
NMS	Neuroleptic malignant syndrome
NSUH	North Shore University Hospital
PHI	Protected health information
PK	Pharmacokinetic
PO	Orally
PoC	Proof of Concept
PR	Partial response
RBC	Red blood cell

---

Abbreviation	Definition
SAE	Serious adverse event
SCT	Stem cell transplantation
shRNA	Small hairpin ribonucleic acid
S/T	Safety/Tolerability
TFP	Trifluoperazine
ULN	Upper limit of normal
UPIN	Unique patient identification number
USP	United States Pharmacopeia

## Study Summary

Title	Phase I/II, Open-Label Study to Determine Safety of Trifluoperazine (TFP) in Adults with Red Blood Cell Transfusion-Dependent Diamond Blackfan Anemia
Short Title	TFP in DBA
Protocol Number	17-0748
Phase	Phase I/II
Methodology	Open-Label, Non-Randomized
Study Duration	18-24 months
Study Center(s)	Single-center/Additional centers may be recruited if enrollment is slow
Objectives	To determine the safety and maximum tolerated dose (MTD) of TFP in red blood cell transfusion-dependent adults with Diamond Blackfan anemia
Number of Subjects	minimum 3, maximum 24
Diagnosis and Main Inclusion Criteria	Transfusion Dependent Adults Diagnosed with Diamond Blackfan Anemia
Study Product, Dose, Route, Regimen	Trifluoperazine (TFP) 1mg, 2mg, 5mg, or 10mg once daily by mouth
Duration of administration	Maximum of 21 days
Reference therapy	Red Cell Transfusion
Statistical Methodology	N/A- dose escalation study for safety/tolerability

## 1 Previous Study History

Has this study ever been reviewed and rejected/disapproved by another IRB prior to submission to this IRB?

No  Yes – if yes, please explain: | |

## 2 Brief Summary of Research

Diamond Blackfan anemia (DBA) is a rare inherited pure red cell aplasia. The two main non-stem cell transplant therapeutic options are corticosteroids and red blood cell (RBC) transfusions. About 80% of DBA patients initially respond to corticosteroids, however, half of the patients cannot continue due to side effects or loss of response. These patients are then typically dependent on RBC transfusions throughout life. Each of these treatments is fraught with many side effects and significant morbidity and mortality are potential consequences of hematopoietic stem cell transplantation (SCT). The majority of individuals with DBA have mutations in genes encoding structural proteins of the small or large ribosomal subunit leading to deficiency of the particular ribosomal protein (RP). Studies in zebrafish with RP deficiencies confirmed the association between RP defects, p53 activation and the appearance of a DBA phenotype. Using the RP deficient zebrafish embryo model, high throughput drug screens have demonstrated a strong hematologic response to several calmodulin inhibitors. One of these chemicals is trifluoperazine (TFP). TFP treatment of a mouse model of DBA also increased the red blood cell count and the hemoglobin (Hb) levels in the mice. TFP is a FDA-approved typical antipsychotic agent that has been available since 1958 with a well-known safety profile. In the United States, TFP is approved for the short-term treatment of generalized non-psychotic anxiety; treatment or prevention of nausea and vomiting of various causes; and, management of psychotic disorders.

In this study we aim to determine the safety and tolerability of TFP in adult subjects with DBA, as a prelude to a possible proof of concept (PoC) trial (as a separate study). TFP's expected dose-limiting toxicity is primarily neurologic (extrapyramidal) when used long-term at typical anti-psychotic doses (range 10-50 mg daily). Non-neurologic adverse effects in

subjects with DBA have not been investigated. We will perform a dose escalation study to define the safety and tolerability of lower doses of this agent in subjects with DBA.

This class of drugs has not been tested specifically in subjects with DBA prior to this study. To mitigate the potential risks of administering TFP to this new population, we will (1) start dosing at dose levels well below those prescribed for psychosis over the past several decades, (2) dose escalate to a maximum of 10 mg daily (the lowest dose typically prescribed for psychosis), and (3) perform weekly safety monitoring. Given the positive signal in DBA animal models and the 60-year clinical experience with higher doses of TFP, this drug warrants a trial in humans to assess tolerability in DBA. If tolerated, this trial will support either a PoC trial of low-dose TFP in DBA, or the advancement of a chemically modified TFP-like drug (to alleviate the neurologic toxicity) for the treatment of DBA.

This is a dose escalation safety and tolerability study to evaluate the presence of TFP-related adverse events in DBA subjects, and to determine the maximum tolerated dose (MTD) of TFP in DBA. The dose escalation strategy is described in [Section 3.5 Dose Rationale and Risk/Benefits](#).

Some first-in-human (FIH) trials may implement an enrollment restriction rule such that two subjects are dosed in a given cohort, and a third subject is not dosed until both of the first two subjects have demonstrated tolerability. For this trial, we have elected not to use such an enrollment restriction design for the following reasons:

- a. This is not a FIH trial: TFP has been in wide clinical use for 60 years.
- b. Our dose levels (1 mg daily, up to max 10 mg daily) are all well within and below the safe range of clinical use. Doses in the 2-6 mg daily range have been shown to have a side effect profile similar to placebo in patients with anxiety ([Mendels, 1986](#)). A randomized clinical trial comparing TFP 15 mg/day vs. placebo in schizophrenic subjects revealed no difference in the rates of severe adverse effects, Parkinsonism or dystonia compared to placebo (Koch, 2014). Doses for psychosis range from 10 mg daily up to 40-50 mg daily, whereas we will dose at 1, 2, 5, and 10 mg daily only.

- c. We will monitor for safety, specifically for any hematologic toxicity and for extrapyramidal/central nervous system (CNS) effects. Dose escalation criteria and actions, as well as subject and cohort stopping rules are detailed in [Section 6 Study Design](#).

### **3 Introduction**

This document is a protocol for a human research study. This study is to be conducted according to US and international standards of Good Clinical Practice (FDA Title 21 part 312 and International Conference on Harmonization guidelines), applicable government regulations, and Institutional research policies and procedures.

### **3.1 Background**

### ***Diamond Blackfan Anemia***

Diamond Blackfan anemia is a rare inherited pure red cell aplasia. Over the past 20 years, mutations have been described in genes encoding both the small and large ribosome associated proteins ([Vlachos, 2014](#); [Draptchinskaia, 1999](#); [Gazda, 2006](#); [Cmejla, 2007](#); [Farrar, 2008](#); [Gazda 2008](#); [Doherty 2010](#)). There is wide variability in clinical and biologic features, familial history, and therapeutic responses. Currently standard therapy includes corticosteroids, RBC transfusions or SCT ([Vlachos, 2001a](#)). Approximately 80% of subjects have an initial response to corticosteroids. Of these subjects, approximately half will fail to achieve a taper to a tolerable steroid dose or have intolerable side effects and will need to discontinue steroid therapy. These subjects and the 20% who do not respond initially to such therapy must be maintained on a chronic RBC transfusion with iron chelation. Chronic transfusions have considerable treatment-related morbidity, most notably iron overload-related organ failure.

SCT has proven to be effective therapy for a select group of subjects. Allogeneic SCT with a histocompatible donor has been performed successfully in a number of subjects. The Diamond Blackfan Anemia Registry of North America (DBAR) experience has been published ([Vlachos, 2001b](#); [Lipton 2006](#)). However, because of remissions (sustained physiologically acceptable erythropoiesis for  $\geq 6$  months without any medication or transfusion) in up to 20% of subjects with DBA, SCT, regardless of donor type, is not consistently offered to corticosteroid-dependent or transfusion-dependent subjects with DBA and no other complications precluding corticosteroid or transfusion use. For many subjects, the lack of a suitable donor does not permit SCT as a therapeutic option, as human leukocyte antigen (HLA)-matched unrelated donor transplants have been associated with mortality and morbidity.

Historically, the lack of truly effective and safe therapy has prompted the investigation of a number of other agents, including high-dose corticosteroids, immunosuppressive therapy (cyclosporine A and antithymocyte globulin), intravenous immunoglobulin, high-dose erythropoietin, interleukin-3, metoclopramide and others; however, these modalities have achieved, at best, anecdotal success ([Vlachos, 2008](#)).

## **3.2 *Investigational Agent - Trifluoperazine***

### **3.2.1 Description**

TFP is a piperazine phenothiazine antipsychotic with 5 mg orally equivalent to 100 mg of oral chlorpromazine, the prototype antipsychotic. TFP is a typical antipsychotic of the phenothiazine chemical class that has been used for the treatment of psychiatric subjects since 1958 ([Rudy, 1958](#)). TFP acts as a dopamine antagonist with antipsychotic and antiemetic activities. TFP blocks CNS postsynaptic mesolimbic dopaminergic D1 and D2 receptors and depresses the release of hypothalamic and hypophyseal hormones and the reticular activating system, thus affecting basal metabolism, body temperature, wakefulness, vasomotor tone, and emesis. In the United States, trifluoperazine hydrochloride tablets, USP, are approved for the short-term treatment of generalized non-psychotic anxiety; treatment or prevention of nausea and vomiting of various causes; and management of psychotic disorders. In part because of its side effect profile, TFP has been largely replaced by second and third generation antipsychotic medications. It is associated with an increased risk of death in elderly subjects treated for dementia-related psychosis. Nevertheless, TFP remains commercially available worldwide and the risks attendant to its use are well understood and generally manageable.

### **3.2.2 Pharmacokinetics**

Trifluoperazine may be administered orally or intramuscularly. This study will only use the oral route of administration. Following administration of the drug, antipsychotic effects are gradual, with considerable individual subject variation, and peak effects may not occur for 6 weeks to 6 months. TFP is readily absorbed from the gastrointestinal tract and is subject to first-pass metabolism in the gut wall. It is metabolized in the liver and excreted in the urine and feces in the form of active and inactive metabolites. TFP is extensively bound to plasma proteins. The drug crosses the blood-brain barrier and its metabolites also cross the placental barrier and are excreted in milk ([MHRA, PAR, 2006](#)).

The single-dose pharmacokinetics (PK) of TFP were determined in 5 healthy adult male volunteers who received TFP 5 mg orally after an overnight fast ([Midha, 1983](#)). Peak TFP concentrations varied widely (range 0.53 to 3.09 ng/mL) and were reached at 2.8 ± 0.5 hours post-dose. The area under the plasma concentration-time curve also differed widely among subjects (range 5.9 to 17.6 ng/mL·h; mean 11.7 ± 2.2 ng/mL·h), suggesting large individual

differences in the extent of pre-systemic TFP elimination. The mean apparent terminal elimination half-life ( $t_{1/2}$ ) of TFP was  $12.5 \pm 1.4$  hours.

More relevant to its function as a potential medication in DBA, TFP also serves as an inhibitor of calmodulin, a multi-functional, intermediate calcium-binding messenger protein.

### **3.3 *Preclinical Data***

### **3.3.1 *In Vivo and In Vitro Activity in DBA Models***

It has been demonstrated that zebrafish embryos with mutations in the *rps29* gene have an erythroid defect, similar to that reported in subjects with DBA ([Taylor, 2012](#)). Furthermore, zebrafish embryos also have endothelial defects as observed by decreased flk1 expression in the intersegmental vessels at 24 hours post-fertilization. Consistent with other animal models of RP mutations, the p53 pathway is activated in the *rps29*-/- embryo, and p53 knockdown in the mutant zebrafish rescues the hematopoietic and endothelial defects ([Taylor, 2012](#)).

In order to identify compounds with the ability to rescue DBA phenotypes *in vivo*, 600 chemicals were screened for their ability to rescue flk intersegmental vessels and reverse the erythroid defect in *rps29*-/- zebrafish embryos. Findings revealed that several structurally diverse calmodulin inhibitors successfully rescued flk staining in the vasculature and Hb levels in the mutant embryo.

TFP was also tested in a murine model of DBA in which mice were transplanted with bone marrow from mice harboring a knock-in allele expressing a doxycycline-inducible *rps19* shRNA ([Montague, 2014](#)). Following engraftment of the transplanted cells, recipient mice were administered doxycycline in drinking water to induce the *rps19* deficiency, p53-induced p21 expression, and severe anemia. Diseased mice then received an intraperitoneal (IP) injection of 5 mg/kg TFP every other day, and after two weeks, bone marrow was collected for quantitative polymerase chain reaction (qPCR) analysis and blood was analyzed for RBC counts and Hb levels. TFP treatment of *rps19*-deficient mice decreased p21 levels, indicating that TFP was hitting the expected target, and significantly increased both RBC counts and Hb levels compared to vehicle-treated controls ([Macari, 2015](#)). Importantly, TFP reduced p53 activity only in the presence of the stress-induced state of *rps19* deficiency, while basal levels of p53 in wild-type mice actually increased modestly. Furthermore, the levels of p53 activity in the *rps19*-deficient mice treated with TFP were not lower than those in wild type mice. TFP was well tolerated in this model, indicating that the TFP dose resulting in improved anemia did not cause gross toxicity.

### **3.4 Clinical Data to Date**

There are no available clinical research data on TFP in subjects with DBA.

A randomized, double-blind, placebo-controlled 4-week trial of low dose TFP (2–6 mg/day) in 415 subjects with generalized anxiety disorder showed that the side effect profile of TFP and

placebo were similar. Anxiety was also significantly improved in the TFP treatment arm ([Mendels, 1986](#)).

A randomized clinical trial comparing TFP 15 mg/day vs. placebo in schizophrenic subjects revealed no difference in the rates of severe adverse effects, Parkinsonism or dystonia compared to placebo. Subjects in the TFP group did experience higher rates of akathisia than did the placebo group. However, significantly more placebo arm subjects left the study early due to poor efficacy, in comparison to TFP-treated subjects ([Koch, 2014](#)).

### **3.5 Dose Rationale and Risk/Benefits**

In an *in vivo* mouse model of DBA, TFP at a dose of 5 mg/kg intraperitoneally every other day reduced apparent p53 activity and raised the RBC count and Hb level after 2 weeks of treatment (Macari, 2016). The murine dose scales allometrically to a daily dose of 12–15 mg of TFP in humans. As the 5 mg/kg dose was the only dose tested in the mouse study, and daily administration of TFP may be more efficacious than every other day dosing, it is possible that a daily dose of 5 mg or less in humans may be efficacious. Given the potential margin of error in the allometric calculation, a maximum dose of 10 mg daily may be tested in this trial.

The starting dose of TFP in subjects with DBA (1 mg) is lower than the starting dose in psychiatric indications, and the maximum TFP dose to be administered to subjects with DBA will not exceed 10 mg. As side effects of TFP have been shown to be dose-/plasma level-related, it is anticipated that the more severe side effects associated with TFP, including extrapyramidal symptoms, will be less likely to occur at doses  $\leq 10$  mg. The two trials cited in section [3.4 Clinical Data to Date](#) also support the likely tolerability of the proposed dose range in this trial ([Mendels, 1986](#); [Koch, 2014](#)).

#### **3.5.1 Dose Escalation**

Up to 4 cohort dose levels of TFP will be studied: 1, 2, 5, and 10 mg/day for up to 21 days each, as tolerated. Cohort A will start at 1 mg/day, and the dose will escalate to 2 mg/day in Cohort B, 5 mg/day in Cohort C, and 10 mg/day in Cohort D. At the start of each cohort, 3 subjects will be enrolled, and an interim analysis (IA) for safety and tolerability will be

conducted after all 3 subjects have completed 21 days of treatment (See [Section 6 Study Design](#) for details). The 21-day time frame is based on the t1/2 from the healthy volunteer 5 mg single dose TFP study ([Midha, 1983](#)), showing that TFP's elimination t1/2 is approximately 12-14 hours. Therefore, steady state is reached approximately 3 days after initiating therapy, and 21 days of therapy provides at least 18 days of exposure at steady state (the 1 and 2 mg doses likely have shorter t1/2 and so steady state will be reached even sooner in the first 2 cohorts).

Whereas some FIH trials may use an enrollment restriction rule such that only two subjects are dosed at a time, this trial will not use such an enrollment restriction design. Please see [Section 2 Brief Summary of Research](#) for the supporting rationale.

### 3.5.2 Dose Modifications

Dose of TFP will be discontinued in case of sustained increase of hemoglobin  $\geq 2$  gm/dL from the previous dose except those attributed to RBC transfusions. Dose should be held in the event of an AE  $\geq$  Grade 3 until resolution (to baseline) or  $\leq$  Grade 1. If AE is not resolved in 7 days then TFP will be discontinued. The guidelines for dose modifications are listed below.

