#### Dose Modification Guidelines

NCI Toxicity-Grade	Event	Action
	Hb $\geq 12$ gm/dL (not associated with RBC transfusion)	Discontinue *
$\geq$ Grade 3	Any adverse event	Dose delay **

\* Subject will discontinue the study drug.

\*\* Delay dose of TFP for up to 7 days or until AE severity improves to  $\leq$  Grade 1 or to Baseline status.

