## 7.2 Exclusion Criteria

Subjects who meet any of the following criteria will not be eligible to participate in the study:

1. Liver: aspartate aminotransferase (AST) > 5 x the upper limit of normal (ULN), alanine aminotransferase (ALT) >5 x ULN, or bilirubin > 5 x ULN.
2. Heart disease (New York Heart Association classification of  $\geq 3$ ; Appendix F).
3. History of angina.
4. Uncontrolled hypertension. If hypertension is considered clinically stable, systolic blood pressure must be <150 mmHg or diastolic blood pressure must be <100 mmHg.
5. Subjects currently responsive to corticosteroids for treatment of DBA.
6. Treatment with another investigational drug or device <56 days pre-study entry. Subjects who participated in an earlier cohort of this trial may participate in a subsequent cohort if (a) they meet all eligibility criteria, (b) did not experience any adverse effects  $\geq$  Grade 3 while on TFP, and (c) discontinued TFP  $\geq$  6 days (10 half-lives) prior to day 1 of the subsequent cohort.
7. Pregnant or lactating females.
8. Any history of severe allergic reaction requiring the use of epinephrine.
9. Known hypersensitivity to the study drug or other phenothiazines.
10. History or presence of extrapyramidal signs.
11. History of cancer.

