## **7.6 Early Withdrawal of Subjects**

### **7.6.1 When and How to Withdraw Subjects**

The following reasons are considered sufficient for withdrawing a subject from the study drug and/or from the study:

- Sustained hemoglobin  $\geq$  12 mg/dL (not influenced by transfusions).
- Any toxicity  $\geq$  Grade 3 (Appendix H).
- Adverse event that, in the judgment of the investigator, may cause severe or permanent harm or that rules out continuation of treatment.
- Hypersensitivity reaction to TFP.
- Withdrawal of consent.
- Death.
- Lost to follow-up.
- Pattern of significant noncompliance.

The reason for subject withdrawal must be documented in the subject chart / source records.

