## 10 Risks to Subjects

Adverse reactions with TFP include drowsiness, dizziness, skin reactions, rash, dry mouth, insomnia, amenorrhea, fatigue, muscular weakness, anorexia, lactation, blurred vision, and neuromuscular (extrapyramidal) reactions. Details regarding extrapyramidal and other adverse reactions with TFP follow:

- **Neuromuscular (Extrapyramidal) Reactions:** These symptoms are characterized by motor restlessness. They may be of the dystonic type, or they may resemble Parkinsonism (described below).
- **Motor Restlessness:** Symptoms may include agitation or jitteriness and sometimes insomnia. These symptoms often disappear spontaneously.
- **Dystonia (Class Effect):** Symptoms of dystonia, prolonged abnormal contractions of muscle groups, may occur in susceptible individuals during the first few days of treatment. Dystonic symptoms include spasm of the neck muscles, sometimes progressing to tightness of the throat, swallowing difficulty, difficulty breathing, and/or protrusion of the tongue. While these symptoms can occur at low doses, they occur more frequently at higher doses of first generation antipsychotic drugs.
- **Pseudoparkinsonism:** Symptoms may include mask-like facies, drooling, tremors, pill-rolling motion, cogwheel rigidity, and shuffling gait.
- **Tardive Dyskinesia:** Tardive dyskinesia is a rare syndrome characterized by rhythmical involuntary movements of the tongue, face, mouth, or jaw (e.g., protrusion of tongue, puffing of cheeks, puckering of mouth, chewing movements). These symptoms may be accompanied by involuntary movements of extremities. In rare instances, these involuntary movements of the extremities are the only manifestations of tardive dyskinesia. Symptoms may persist for months or years and, while they gradually disappear in some subjects, they may be irreversible in others. The risk appears to be greatest in elderly subjects (especially women) on prolonged, high-dose therapy. There is no known effective treatment for tardive dyskinesia. It has been reported that fine vermicular movements of the tongue may be an early sign of the syndrome and if the medication is stopped at that time the syndrome may not develop.
- **Adverse Reactions Reported with TFP or Other Phenothiazine Derivatives:** Adverse effects with different phenothiazines vary in type, frequency, and mechanism of

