## **15.4 Stopping Rules**

The stopping rules are as follows:

Scenario 1: The occurrence of extrapyramidal symptoms, symptoms suggestive of tardive dyskinesia (including vermicular movements of the tongue), neuroleptic malignant syndrome or any SAE or treatment-emergent AE  $\geq$  Grade 3 felt to be causally related to TFP in a single subject:

- Rule: Treatment will be immediately stopped in that subject and the subject will be discontinued from the study.

Scenario 2: The occurrence of the extrapyramidal symptoms, symptoms suggestive of tardive dyskinesia (including vermicular movements of the tongue), neuroleptic malignant syndrome or the same SAE or treatment-emergent AE  $\geq$  Grade 3 felt to be causally related to TFP in more than 1 subject:

- Rules:
  - a. Treatment will be immediately stopped in those subjects and those subjects will be discontinued from the study.
  - b. If the 2 or more subjects are in Cohort A, the trial will be stopped; no MTD will be declared.
  - c. If the 2 or more subjects are in Cohort B, the study will be stopped, and 1 mg/day will be declared the MTD.

- d. If the 2 or more subjects are in Cohort C, the study will be stopped, and 2 mg/day will be declared the MTD.
- e. If the 2 or more subjects are in Cohort D, the study will be stopped, and 5 mg/day will be declared the MTD.

Scenario 3: Hemoglobin > 12 mg/dL in a subject sustained for more than 7 days (not associated with RBC transfusion)

- Rule: The subject will be considered a complete responder, treatment will be discontinued, and the duration of the effect will be monitored until day 29 after start of treatment.

In addition to the stopping rules, a subject may be discontinued by the investigator at any time for failure to comply with protocol requirements, in the event that the investigator feels that continuation in the study poses a risk to the health of the subject, or if the subject withdraws consent.

The reason for treatment discontinuation must be documented in the subject chart / source records.

The trial will be stopped, as noted above, if more than one subject experiences the occurrence of the extrapyramidal symptoms, symptoms suggestive of tardive dyskinesia, neuroleptic malignant syndrome, the same SAE or treatment-emergent AE  $\geq$  Grade 3 felt to be causally related to TFP at the lowest dose level.

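### For a TFP-related event of Grade 3 or higher, Section 3.5.2 directs a hold with implied restart, while Section 15.4 requires a permanent stop

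*Combined protocol and SAP*

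**What the plan says.** Three sections address the individual subject who has an event of Grade 3 or higher.

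- **Section 3.5.2, text.** "Dose should be held in the event of an AE" of Grade 3 or higher, until it returns to baseline or to Grade 1 or lower. Then: "If AE is not resolved in 7 days then TFP will be discontinued". Causality is not mentioned.
- **Section 3.5.2, table.** The row for any adverse event of Grade 3 or higher gives a dose delay; the hemoglobin row above it gives discontinuation. The footnote reads "Delay dose of TFP for up to 7 days or until AE severity improves to" Grade 1 or lower, or baseline.
- **Section 7.6.1.** Any toxicity of Grade 3 or higher is in a list introduced by "The following reasons are considered sufficient for withdrawing a subject from the study drug and/or from the study". That permits withdrawal without requiring it.
- **Section 15.4, Scenario 1.** For extrapyramidal symptoms, signs of tardive dyskinesia, neuroleptic malignant syndrome (NMS), or an SAE or Grade 3 or higher treatment-emergent event judged related to TFP: "Treatment will be immediately stopped in that subject and the subject will be discontinued from the study".

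Section 2 says that "subject and cohort stopping rules are detailed in" Section 6. The available text of 6.1 has cohort rules and a hemoglobin stop, but no rule for a single subject with a Grade 3 or higher event. Figure 1 and part of the Cohort A and B text are not shown.

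**The concern.** In a safety study, the dose action after a severe drug-related event should be unambiguous. Section 3.5.2 holds the dose-modification table, so it is a natural place for site staff to look. Read alone, it makes discontinuation depend on whether the event resolves, not on whether the drug caused it. A subject with a related event that settles in a few days could be dosed again, although 15.4 removes that subject from treatment. What is at stake is avoidable re-exposure of an individual subject.

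Two smaller matters of the same kind sit nearby. The hemoglobin stop is stated in several forms, two of them in the wrong unit. Sections 2 and 7.5 also promise weekly monitoring that the visit schedule does not contain.

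**Working it through.** The plan gives no figure for this point, so the check is mainly a comparison of text.

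**1. Where the rules part company** (event of Grade 3 or higher)

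| Event | 3.5.2 | 15.4 Scenario 1 |
|---|---|---|
| Related, resolves within 7 days | Hold, restart implied | Immediate permanent stop |
| Related, unresolved at 7 days | Hold, then discontinue | Immediate permanent stop |
| Unrelated, not a named neurologic event | Hold, restart implied if resolved | Not triggered |

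The first row is the conflict. The named neurologic triggers in 15.4 carry no stated grade threshold, and the causality phrase can be read as applying only to the SAE and adverse-event clause. On that reading they require a stop whatever the grade or attribution.

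**2. Doses at issue (illustration).** Assume that the last dose is Day 21 and that held doses are not made up; the protocol is silent on make-up. With first held dose on Day *d* and *h* days held (1 to 7), doses after restart = 22 − *d* − *h*, not below 0.

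- *d* = 4: 22 − 4 − 1 = 17, down to 22 − 4 − 7 = 11.
- *d* = 11: 22 − 11 − 1 = 10, down to 22 − 11 − 7 = 4.
- *d* = 15, *h* = 7: 0.
- Under 15.4: 0 for every *d*.

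**3. How often.** The documents give no rate of related Grade 3 or higher events. At assumed rates of 2%, 5%, 10% and 20% per subject, the chance of at least one among the first 3 subjects of a cohort, 1 − (1 − *p*)³, is 6%, 14%, 27% and 49%. These are not estimates for this trial.

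**4. Escalation.** Section 6.1 counts subjects with toxicity of Grade 3 or higher. The subject is counted when the event occurs, whether or not dosing resumes. The enrolment range is also untouched: minimum 3, maximum 4 × 6 = 24.

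**5. Hemoglobin stop**

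| Place | Trigger | Duration |
|---|---|---|
| 3.5.2 text | rise ≥ 2 g/dL from the previous dose | sustained, undefined |
| 3.5.2 table | ≥ 12 g/dL | none |
| 6.1 | > 12 g/dL | none |
| 7.6.1 | ≥ 12 **mg/dL** | sustained, undefined |
| 15.4 Scenario 3 | > 12 **mg/dL** | more than 7 days |

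12 mg/dL is 0.012 g/dL, a factor of 1000 too low. If the single reading in 6.1 binds, the durations in 7.6.1 and 15.4 have no effect as stopping criteria.

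**6. Visits.** Section 9 and Appendix A schedule Days 1, 11, 22 and 29, so the gaps up to Visit 3 are 11 − 1 = 10 and 22 − 11 = 11 days. At the Appendix A window limits the shortest are 10 − 2 = 8 and 20 − 12 = 8 days. Neither is weekly. Only the post-treatment gap (29 − 22 = 7 days) is.

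**The case against.** The best defence is that the rules can be reconciled. Section 3.5.2 uses *should* and calls its table guidelines; 15.4 is headed as stopping rules and uses *will*. A site could hold at once under 3.5.2 and stop permanently under 15.4 once the event is judged related, breaching neither. Resumption is implied, not stated, and there is no rechallenge procedure. This makes 15.4 the likely intent. It does not remove the conflict, because 3.5.2 ties discontinuation to non-resolution and its table covers every adverse event of that grade.

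Section 7.2, criterion 6(b), points the same way: entry to a later cohort requires that the subject "did not experience any adverse effects" of Grade 3 or higher on TFP. The support is modest, since that rule concerns a later cohort, usually at a higher dose.

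Several stronger readings are tempting but unsupported:

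- **That the protocol has no ranking rule anywhere.** Part of 6.1 is not shown, so this can be said only of the available text.
- **That many early re-exposures should be expected.** Section 10 says dystonia "may occur in susceptible individuals during the first few days of treatment", which suggests an early onset. But dystonia is extrapyramidal and 15.4 names that category expressly, so it is where the stop is clearest. Section 3.5 also expects severe effects to be less likely at these doses.
- **That the 3+3 design anticipates such subjects because it can continue after 1 toxicity in 6.** That count carries no causality condition in the available text, whereas the conflict concerns related events only.
- **That the more-than-7-days hemoglobin rule is unworkable.** On scheduled draws it can be confirmed before dosing ends only if Visit 3 falls on Day 20 or 21. Appendix A, note b, allows extra laboratory tests, and Scenario 3 also serves to label a complete responder.
- **That sites will diverge.** The Study Summary says single-center unless enrollment is slow, while 6.1 says multi-center. Divergence is possible but not shown.

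**Conclusion.** The inconsistency is real and confined to dosing of the individual subject. For a related event of Grade 3 or higher that resolves within 7 days, 3.5.2 implies restart, 7.6.1 leaves withdrawal optional, and 15.4 requires a permanent stop. Section 15.4 is probably what the sponsor intends, but the reader has to infer it.

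The difference is some further doses against none, and it shrinks to nothing for a full 7-day hold starting on or after Day 15. The dose counts rest on assumed onset, hold length and no make-up of held doses; the event rates are assumed outright. Neither should be read as a forecast. A reader might infer that the MTD or the escalation decision is compromised; the documents do not support that, because the 6.1 count does not depend on resumption.

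The correction is worth making because it protects subjects at almost no cost. The hemoglobin and weekly-monitoring points are minor clarifications. The mg/dL entries are evident slips; the differing operators and durations are genuine ambiguities.

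**What to change.** **Main change, in 3.5.2 (text and table):**

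1. Hold TFP at once for every adverse event of Grade 3 or higher, pending causality assessment.
2. If the event is judged related to TFP, or is any Scenario 1 event (extrapyramidal symptoms, signs of tardive dyskinesia, NMS, a related SAE), stop permanently under 15.4.
3. Allow restart only for events judged unrelated that return to baseline or to Grade 1 or lower within 7 days.
4. Add a cross-reference to this rule in 7.6.1.

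The hold must stay in place while causality is open. Limiting it to events already judged unrelated would leave subjects on drug during that assessment.

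**Minor changes:**

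- Correct mg/dL to g/dL in 7.6.1 and 15.4.
- State one hemoglobin stopping rule (threshold, operator, duration, and whether the 2 g/dL rise is a separate trigger) and refer to it from 3.5.2, 6.1, 7.6.1 and 15.4. If a single-reading stop is chosen, keep the more-than-7-days condition only as the complete-responder label. The threshold is the sponsor's clinical choice.
- Replace *weekly* in Sections 2 and 7.5 with Days 1, 11, 22 and 29.

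**Cost:** one wording amendment to Sections 2, 3.5.2, 6.1, 7.5, 7.6.1 and 15.4. No added subjects, visits or blood draws. The immediate hold is already in 3.5.2.
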